5. DATA COLLECTION

This study involves a total of seven participant visits. Visits will occur as follows: 1) Orientation Visit (pre-study). 2) Clinic Visit 1 (Baseline; Day 1 of Feeding Period 1), 3) Midpoint Visit 1 (~Day 10 of Feeding Period

1), 4) Clinic Visit 2 (Day 22, the day after the end of Feeding Period 1), 5) Clinic Visit 3 (Day 1 of Feeding Period 2), 6) Midpoint Visit 2 (~Day 10 of Feeding Period 2), and 7) Clinic Visit 4 (end of study; Day 22 the day after the end of Feeding Period 2). At the Orientation Visit, the study Lifestyle Questionnaire will be completed. At all clinic visits, participants will undergo assessments of anthropometrics, and on clinic visits 1, 2 and 4 they will bring stool and urine samples collected at home and will provide fasting blood.

Twelve-hour fasting blood. Fasting blood samples will be collected on Day 1 of the first Feeding period, and on Day 22 of the first feeding period and Day 22 of the second feeding period. Vacutainers will be labeled with participants' study ID and date, processed per standard protocol and stored at -80°C.

Stool sample: Stool samples will be collected by participants at home prior to Clinic Visits the beginning (Clinic Visit 1) and end of Feeding Period 1 (Clinic Visit 2) and the end of Feeding Period 2 (end of study, Clinic Visit 4).

Urine sample: 24-hour urine samples will be collected by participants at home prior to Clinic Visits at the beginning (Clinic Visit 1) and end of Feeding Period 1 (Clinic Visit 2) and the end of Feeding Period 2 (end of study, Clinic Visit 4).

Questionnaires:

Lifestyle Questionnaire. Date of birth, self-identified race/ethnicity, gender identity, education, smoking, alcohol use, recreational drug use, over-the-counter and prescription drug use, dietary supplement use, physical activity levels and general health history will be collected at the Visit 1 (self-administered questionnaire).

Daily meal check-off forms. All participants will complete study provided meal check-off forms to record and quantify daily meals consumed each day during both feeding periods.

5.1 Outcomes

5.1.1 Metabolome

Fasting blood, 24-hour urine, and fecal samples collected at baseline and after each diet period for each participant. Shifts in the metabolome will be characterized by conducting metabolomics assays on the blood urine, and fecal samples and comparing the readouts between the HEI-2015 and HEI-2015-M diets.

5.1.2 Microbiome

Stool DNA will be extracted from the fecal samples collected at baseline and after each diet period for each participant. Modulation of the gut microbial community will be characterized by 16S rRNA gene sequencing of the extracted genomic DNA and comparing the readouts between the HEI-2015 and HEI-2015-M diets.

In addition, digital droplet PCR assays will be conducted to measure changes in the genes for *butyrate kinase (buk)* and *nitrate reductase (narG)*, and archival samples will be collected to conduct microbial growth experiments.

5.1.3 Anthropometrics

Height and waist circumference will be measured at the orientation visit only, and weight will be measured at the beginning, midpoint and end of each feeding period for each participant.

6. PARTICIPANT RISKS AND BENEFITS

6.1 Potential Risks

1. Participants may experience a little discomfort or have a temporary bruise from having blood drawn. Occasionally a participant may feel lightheaded or feel faint when having blood drawn since blood is drawn after a 12 hour fast. The amount of blood drawn for this study does not exceed 50 ml total over the 11 week study and does not occur more than twice weekly.

2. Some participants may feel that coming to study visits and consuming only study-provided foods for two 3-week periods is burdensome.
3. Some participants may find it inconvenient or uncomfortable to collect their urine and stool.

6.2 Protection Against Risks

In the event that this research activity results in an injury, medical treatment will be available, including first aid, emergency treatment and follow up care, as needed. All procedures involving blood collection and anthropometry will be done at the Fred Hutch Prevention Center Clinic. Participants will collect urine and stool samples at home. Food is carefully and safely prepared under highly controlled conditions. Trained staff will be available to assist should a medical emergency occur. An MD licensed in Washington State is the Prevention Center Director. Participants will be informed in the written consent form that payment for any such treatment must be provided by the individual and/or the individual's insurance company.

1. Participants may experience a little discomfort, bruising, fainting or phlebitis from having blood drawn. We will minimize these risks by making sure that all blood draws are conducted by well-trained nurses, medical assistants, or phlebotomists at the Fred Hutch Prevention Center. Participants will be asked before the blood draw if they have experienced problems with blood draws in the past, and they will be offered an opportunity to lie down during the procedure if they wish. After the blood draw is complete, participants will remain seated, applying pressure to the site of venipuncture. If a participant feels faint, they will be instructed to lie down until the feeling goes away. We provide a small snack and fluids after the blood draw. In our experience, blood draws performed in this manner are well tolerated, and any side effects are minimal.
2. We will make every effort to schedule participants to come to the Fred Hutch at times that are convenient for them; most participants find that morning appointments work well for the fasting blood draws. During the approximately 3-week "washout" period, participants will be allowed to eat whatever foods they like.
3. Participants will be provided all necessary supplies as well as instructions to help in the collection of stool and urine specimens. In addition, they will be provided with opaque bags to discretely carry specimens to their study visit. Study staff will be available by telephone should the participant have any questions or complications when collection these specimens.

6.3 Benefits

The data generated from this proposed clinical trial will provide essential information for participants regarding the effects of red and processed meat in the context of an overall healthy dietary pattern on the metabolome and microbiome of healthy adults.

The research we propose here is important because if a specific nutritional intervention can be shown to improve measures of the metabolome and the microbiome, then it will provide compelling preliminary data to then launch a larger clinical trial which could, potentially, have far reaching implications for thousands healthy adult members of the general population. Thus, with minimal risk to study participants, we will generate data that will be beneficial to general dietary guidance related to health promotion and disease prevention – including cancer prevention.

Overall, using this rigorous study design (randomized cross-over feeding trial), we have attempted to minimize any potential risks to study participants, whilst maximizing the amount of important scientific data that can be generated and ultimately shared with the scientific community and the general public.

6.4 Compensation

Participants will be paid \$100 total, \$25 at the end of the first feeding period and \$75 at the end of the second feeding period to help compensate for time and travel. All food will be provided for the two feeding periods.

6.5 Alternatives

Alternatives to participating in this research study include not participating.

7. DATA ANALYSIS PLAN

This trial identifies (1) the extent and nature of metabolomic shifts and (2) as a secondary aim, modulation of the gut microbiome when consuming a standard HEI-2015 diet compared to a HEI-2015-M diet. We expect that daily intake of red and processed meat will induce shifts in the metabolome detected in blood and urine samples, and secondarily in the gut microbiome detected in extracted fecal DNA. Under the NIH R21 mechanism, it is considered a preliminary trial.

Statistical Analysis for the Primary Aim. Aim 1 identifies metabolomic markers that differ between HEI-2015 and HEI-2015-M. Metabolites from NMR and LC/MS-MS platforms will be used to allow greater coverage of the metabolome and as shown feasible by [name] and others.⁹⁸ Metabolite levels are normalized by dividing by the batch's median value followed by removing metabolites with >25% CVs in the embedded blinded duplicates as well as those with >20% missing values (expected at 5-10% of total). Next, we will use unsupervised principal components analysis (PCA) to visually examine the data patterns and variability. We then apply supervised orthogonal partial least squares discriminant analysis (OPLS-DA) to identify candidate biomarkers that may differ by diet arm. VIP (variable importance in projection) scores >2 will be retained. For each identified metabolite, separate linear mixed models will be fit to examine fold-changes in end of diet period metabolite levels by HEI-2015 and HEI-2015-M, adjusting for baseline. In the cross-over design each participant is their own control, minimizing noise in intra-individual variation in endogenous metabolites. The cross-over design also minimizes confounding by age, BMI, and diet order, but models are run with and without these adjustments. The Benjamini-Hochberg approach controls for false discovery rate (FDR) <0.10.⁹⁹

Statistical Analysis for the Secondary Aim. To account for different sequencing depths, we will initially apply the centered-log ratio (CLR) transformation to each sample after replacing any zero counts by 1 or a small imputed value.¹⁰⁴ We will first gauge the overall strength of microbial signal by applying a microbiome-wide kernel-association test fusing a GLMM-MiRKAT¹⁰⁵ with respect to the weighted UniFrac distance.^{106, 107} Analyses will account for the crossover study design using linear mixed models with outcome of either genera, alpha diversity, or genes for butyrate kinase (*buk*) or nitrate reductase (*narG*), adjusting for baseline. As with Aim 1, we will conduct analyses with and without adjustment for age, BMI, diet order and other covariates. We will use Benjamini-Hochberg approach to account for FDR <0.10.⁹⁹ Based on our studies⁶² and that of others⁵⁸ we expect to have 80% power to detect β coefficients in the linear mixed models in the range of 0.3- 04 for differences between diets at $p < 0.05$. Primary analysis focuses on three genera associated with butyrate production and three genera associated with nitrate reduction. All genera will be examined in exploratory analysis.¹⁰⁸

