2. STUDY DESIGN

Overview. This is a randomized cross-over feeding trial to test whether red and processed meat consumption, in the context of a controlled diet based on HEI-2015, will cause shifts in the metabolome and the microbiome compared to a controlled HEI-2015 diet with no red or processed meat. Twenty healthy adults will complete two feeding periods, in random order of 21 days each with an approximately 21-day washout between feeding periods (**Figure 1**). Study meals are prepared at the Fred

Figure 1. Study design

Hutch Human Nutrition Laboratory (HNL). Participants attend seven clinic visits at the Fred Hutch Prevention Center Clinic: an orientation visit at which consent and randomization will occur; three visits to complete fasting blood draws and to deliver 24-hour urine and stool specimens collected at home; one visit to initiate feeding period 2 and two mid-point visits to check for weight stability. The collected biospecimens are used for study outcomes.

Healthy volunteers will be recruited for this study. Healthy volunteers are well-suited for this study so results will be generalizable.

The study is supported by NIH's R21 mechanism, which is designed to collect preliminary data to support larger trials.

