7.1 Sample Size for the Primary Aim

The sample size is based on the primary aim. For this pilot trial with a fixed sample size of 20 participants, we estimate that we expect to have 80% power to detect fold changes between diets of ± 0.20 for blood and urine metabolites. Power calculations used MetSizeR.¹¹⁰ Tests are 2-sided $\alpha = 5\%$.

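### A VIP >2 screen, with input, scaling, pairing and validation unstated, decides which metabolites are ever tested and can drop true diet effects

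*Combined protocol and SAP*

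**What the plan says.** The primary-aim analysis in section 7, repeated in the synopsis under Primary Analysis Plan, runs in sequence: batch-median normalisation and quality filters, PCA for inspection, then OPLS-DA. On the last step: "We then apply supervised orthogonal partial least squares discriminant analysis (OPLS-DA) to identify candidate biomarkers that may differ by diet arm". The rule that follows is: "VIP (variable importance in projection) scores >2 will be retained". Linear mixed models, adjusted for baseline, are then fitted separately to each metabolite so identified. Benjamini-Hochberg at 0.10 is applied, but the set it covers (all metabolites or only the retained ones) is not stated.

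The own-control rationale comes after the mixed-model sentence: "In the cross-over design each participant is their own control, minimizing noise in intra-individual variation in endogenous metabolites". It is not tied to the OPLS-DA. Nothing says whether the OPLS-DA uses raw end-of-diet levels, changes from baseline or within-person differences. Variable scaling, number of components, cross-validation and permutation testing are also absent. By contrast, the secondary-aim text says explicitly that the microbiome analyses take the crossover into account.

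Section 7.1 gives the power: "we expect to have 80% power to detect fold changes between diets of ± 0.20 for blood and urine metabolites". It does not mention the VIP screen.

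**The concern.** The primary aim is to find metabolites that differ between diets. A metabolite that fails the VIP threshold never reaches the model that compares each participant with themselves, so the screen's sensitivity is a ceiling on the sensitivity of the whole analysis. If the screen compares the two diets without pairing, between-person variation returns to the yardstick, and the metabolites for which a crossover helps most are the likeliest to be lost. VIP is also relative: each metabolite's score depends on how many others respond. At stake are the completeness of the primary result and, through it, the preliminary data for the larger study.

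**Working it through.** **Inputs from the documents.** The design is a two-period crossover: "Twenty healthy adults will complete two feeding periods, in random order of 21 days each". That gives 20 pairs, or 20 × 2 = 40 end-of-diet profiles per biofluid. The threshold is VIP >2 and the FDR level is 0.10. No SD, within-person correlation, metabolite count or responsive share is stated, so those below are assumptions.

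**The plan's own figure.** The 80% power can be neither reproduced nor refuted without an SD. With 20 pairs and a two-sided 5% test, 80% power needs a paired effect of dz = 0.66 (mean difference divided by SD of the difference). A shift of 0.20 then implies an SD of the difference of 0.20 / 0.66 ≈ 0.30. At SD 0.4 the paired power is 56%, and at 0.5 it is 40%. None of these allows for a prior screen.

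**What VIP ranks.** With one two-class outcome y, the OPLS predictive weight is proportional to X'y, and predictive VIP = √p × |w| with w of unit length. On unit-variance-scaled, unpaired samples this ranks metabolites by |mean diet difference| / total SD. Let ICC be the within-person correlation and σw the within-person SD. The mean difference is dz × √2 × σw and the total SD is σw / √(1 − ICC), so the ratio is dz × √(2(1 − ICC)). For equal paired evidence the score shrinks by √(1 − ICC): 0.89 at ICC 0.2 and 0.45 at ICC 0.8.

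**Simulation 1.** Assumed: 200 metabolites, within-person correlation uniform on 0.2 to 0.9, each true metabolite with dz = 1.0, unit-variance scaling. High correlation means above 0.65. Share of true metabolites passing VIP >2:

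| Shifted, of 200 | Unpaired: high-correlation | Unpaired: all true | Within-person centred: high-correlation | Within-person centred: all true |
|---|---|---|---|---|
| 10 | 61% | 85% | 94% | 94% |
| 20 | 40% | 71% | 83% | 83% |
| 40 | – | 45% | – | 35% |
| 60 | – | 24% | – | 2% |

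With no screen and Benjamini-Hochberg at 0.10 over all metabolites, 88% to 98% of true metabolites are found across 10 to 60 shifted.

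**Simulation 2.** Assumed: 300 metabolites, 10% responsive, half at ICC 0.2 and half at 0.8, unit-variance scaling.
- dz = 0.66 (80% paired power per metabolite): the unpaired screen passes 79% of low-ICC and 12% of high-ICC true metabolites; the paired screen passes 54% and 52%.
- dz = 1.0: unpaired 96% and 27%; paired 82% and 83%; no screen 93% and 94%.

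**Where the pairing loss goes away.**
- Common ICC of 0.5: 83% unpaired against 83% paired.
- Centring only, with equal within-person SDs: 84% low-ICC against 85% high-ICC. The weight is then proportional to dz × √2 × σw, which does not involve ICC. Under the same conditions Pareto scaling gives 93% against 65%.
- Change from the shared baseline: each change has variance 2σw² and the two changes have covariance σw², a correlation of 0.5 for every metabolite. In the setting of simulation 1, 94% (10 shifted) and 84% (20 shifted) of high-correlation true metabolites then pass.

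**Why the threshold fails whatever the pairing.** Mean VIP² is 1, so the squares sum to p. If k metabolites exceed 2, then 4k < p, so k < p/4. With 60 of 200 shifted, 30% of metabolites are true, and they cannot all pass.

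**Validation.** With no diet effect at all and 300 metabolites, about 17 still pass the unpaired screen. About 8 are declared if Benjamini-Hochberg covers only the retained set, against about 0.1 if it covers all 300.

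**The case against.** The best counter-argument is that the plan never says the OPLS-DA runs on 40 samples treated as independent. The synopsis defines the primary endpoint relative to each participant's baseline, and section 4.6 says end-of-diet samples are adjusted for baseline. On change-from-baseline input the pairing loss vanishes. This stands. A reader might infer that the plan chose to ignore the pairing and therefore discards true metabolites; the documents do not support that. They leave input, scaling and pairing open, so the most that can be said is that the screen can discard them.

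Two other tempting readings also fail. One is that missing cross-validation contributes to the loss of true metabolites. It does not: it leaves overfitting unchecked and can admit false ones. The other is that pairing the OPLS-DA cures the problem. With VIP >2 retained, centring does worse than the unpaired form once many metabolites respond (35% against 45% with 40 shifted, 2% against 24% with 60), and it lowers the passage of low-ICC true metabolites (96% to 82% at dz = 1.0).

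It can also be said that this is a pilot seeking candidates and that inference rests on the mixed models. That does not answer the point, because a search for candidates most needs sensitivity and the models see only what the screen lets through.

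**Conclusion.** The concern holds in a conditional form. What is certain from the text is that a hard VIP threshold decides which metabolites are tested, ahead of the only step where pairing enters, and that the OPLS-DA is under-specified. The loss of metabolites with stable between-person differences requires unpaired, unit-variance-scaled end-of-diet input and correlations that differ between metabolites. Over all true metabolites it is then moderate when few respond: compared with within-person centring, 9 points with 10 shifted (94 − 85) and 12 points with 20 (83 − 71). It is larger in the high-correlation group. The relative nature of the threshold does not depend on pairing, and it dominates once a substantial share of metabolites respond. With only 10 shifted, dropping the screen gains little overall (88% found against 85% passing the unpaired screen). All sizes rest on assumed metabolite counts, correlations, effects and responsive shares. This should be changed before analysis, because a stated rule is replaced by a better one at analysis cost only.

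**What to change.** In section 7 and the synopsis, remove VIP >2 as a condition for testing. Fit the mixed model to every metabolite that passes quality control, and state that Benjamini-Hochberg at 0.10 covers that full set.

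Keep OPLS-DA and VIP as a description of the multivariate pattern. State the input matrix and scaling. Use a within-participant (multilevel) form, keep both samples of a person in the same cross-validation fold, and permute diet labels within person. Do not rely on pairing the OPLS-DA while the VIP screen stays. The power statement in section 7.1 should refer to the analysis as revised.

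The cost is plan wording and code, with no new data. More models are fitted, and the Benjamini-Hochberg correction covers a larger set.

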SUBJECT SELECTION CRITERIA: Exclusion Criteria	Exclusion Criteria : 1. Known allergy to red or processed meat 2. Vegetarian or vegan 3. Religious or personal reason(s) to avoid red or processed meat 4. Pregnant and/or exclusively breastfeeding 5. Alcohol or recreational drug abuse

DURATION OF SUBJECT PARTICIPATION AND DURATION OF STUDY	Subjects will participate in the study for 11 weeks. The total duration of the study is expected to be 1.5 years
PRIMARY ENPOINTS	Primary Aim 1: Compare intervention effect of each feeding period on shifts in the metabolome as detected in blood and urine samples relative to baseline for each participant.
SECONDARY ENDPOINTS	Secondary Aim: Compare intervention effect of each feeding period on shifts in the gut microbial community as detected by 16S rRNA gene sequencing and digital droplet PCR relative to baseline for each participant.
STATISTICS Primary Analysis Plan	Statistical analysis for primary Aim 1 (metabolome). Aim 1 identifies metabolomic markers that differ between HEI-2015 and HEI-2015-M. Metabolites from NMR and LC/MS-MS platforms will be combined to allow greater coverage of the metabolome. Metabolite levels are normalized by dividing by the batch's median value followed by removing metabolites with >25% CVs in the embedded blinded duplicates as well as those with >20% missing values (expected at 5-10% of total). Next, we use unsupervised principal components analysis (PCA) to visually examine the data patterns and variability. We then apply supervised orthogonal partial least squares discriminant analysis (OPLS-DA) to identify candidate biomarkers that may differ by diet arm. VIP (variable importance in projection) scores >2 will be retained. For each identified metabolite, separate linear mixed models are fit to examine fold-changes in end of diet period metabolite levels by HEI-2015 and HEI-2015-M, adjusting for baseline. In the cross-over design each participant is their own control, minimizing noise in intra-individual variation in endogenous metabolites. The cross-over design also minimizes confounding by age, BMI, and diet order, but models are run with and without these adjustments. The Benjamini-Hochberg approach controls for false discovery rate (FDR) <0.10.

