4.6 Clinic Visit 3 (Feeding Period 2, Day 1)

After concluding an approximately three-week washout period, participants return to the clinic on Day 1 of Feeding Period 2 for repeat anthropometric measurements (weight and waist circumference). To conserve resources, blood, urine and stool are not collected again at this visit; end of study diet samples are adjusted for baseline samples as we have done in other feeding studies.^{59, 62} Using the study calendar, study staff review instructions for the next three weeks (Feeding Period 2), meal pick-up/delivery, proper food storage and reheating and answer any participant questions. Clinic visit 3 concludes with participants being provided the first three days of Feeding Period 2 meals and corresponding daily meal check-off forms.

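### Primary aim: Benjamini-Hochberg applied to metabolites already picked with the diet label does not hold the stated FDR below 0.10

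*Combined protocol and SAP*

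**What the plan says.** The primary analysis appears in the Synopsis (Statistics, Primary Analysis Plan) and in Section 7, with the same sequence:

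- Normalisation is by batch only: "Metabolite levels are normalized by dividing by" the batch median. Metabolites with a CV above 25% in blinded duplicates, or more than 20% missing, are dropped. No scaling for the multivariate step is given.
- After a PCA for inspection, the plan uses "orthogonal partial least squares discriminant analysis (OPLS-DA) to identify candidate biomarkers that may differ by diet arm".
- The screen and the tests follow directly: "VIP (variable importance in projection) scores >2 will be retained. For each identified metabolite, separate linear mixed models will be fit". The Synopsis has the same step: "For each identified metabolite, separate linear mixed models are fit to examine fold-changes in end of diet period metabolite levels".
- Error control is one sentence: "The Benjamini-Hochberg approach controls for false discovery rate (FDR) <0.10".

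The number of tests entering BH is not stated, and no hold-out sample, permutation step or selection-adjusted test is described. The primary endpoint is "shifts in the metabolome as detected in blood and urine samples relative to baseline for each participant". There is one end-of-period sample set per diet and one baseline per participant; Section 4.6 says of the start of period 2: "To conserve resources, blood, urine and stool are not collected again at this visit". For the secondary aim, by contrast, Section 7 fixes a primary set in advance: "Primary analysis focuses on three genera associated with butyrate production and three genera associated with nitrate reduction".

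**The concern.** BH holds the FDR at its nominal level when the p-values of true nulls in the family behave as uniform. The CV and missingness filters ignore diet, so they do no harm. The VIP gate does not ignore diet: it keeps a null metabolite because its levels happened to differ between diets in these 20 people. The mixed model then tests that same difference on the same samples. Null p-values among the survivors are therefore already small, and BH over the survivors alone cannot know how many metabolites were screened out.

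This is the declaration rule for the primary aim. The Synopsis (Rationale for Number of Subjects) says the results are preliminary data for a larger grant application. A list with a large share of false entries, reported as FDR <0.10, would mislead that application.

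**Working it through.** **1. The plan's own figure.** Section 7.1 gives 80% power at n = 20 for fold changes of ±0.20, two-sided 5%. No SD or other MetSizeR input is given, so this cannot be reproduced. A paired t-test with n = 20 reaches 80% power at a standardised paired difference d = 0.66, which implies an SD of the within-person difference of 0.20/0.66 ≈ 0.30. I use this only to set an effect size.

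**2. What the gate does.** With m metabolites and one predictive component, VIP_j = √m·|w_j| with Σw_j² = 1, so the mean of VIP² is 1.

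- With no diet effect and autoscaled data, the w_j are roughly normal, so the share with VIP > 2 is about P(|Z| > 2) = 4.55%. For an assumed m = 300, about 300 × 0.0455 ≈ 14 survive, roughly those already near p < 0.05.
- BH over those 14 declares all of them if the largest p is at most 0.10 × 14/14 = 0.10.
- BH over all 300 would need the 14th smallest p to be at most 0.10 × 14/300 = 0.0047.
- If k metabolites pass, 4k < m. At most 25% can ever pass, however broad the diet effect.

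**3. Simulation inputs.** From the documents: 20 participants, two diets, VIP > 2, BH at 0.10, one baseline each. Assumed, because the documents are silent: metabolite count, scaling (autoscaled, Pareto, none), correlation (independent, blocks, factors), intraclass correlation, and VIP from one, two or three components. The diet test is a paired t-test. With one baseline per person and complete pairs, baseline cancels from the diet contrast. In 60 fitted mixed models with baseline as covariate the diet estimate equalled the paired difference, and t agreed to 5e-5 in the 54 with non-zero participant variance.

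**4. No diet effect** (50–1000 metabolites, 216 settings, 600 runs each). Chance of at least one false declaration:

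| BH family | Result |
|---|---|
| Survivors, 1- or 2-component VIP | 22–100%, median 75% |
| Survivors, 3-component VIP | 6–100% |
| All metabolites | 7–15%, mean 9.5% |
| Gate kept, full count as denominator | 1–12% |

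The survivor rule exceeded 10% in 214 of the 216 settings. Both exceptions were autoscaled with a three-component VIP.

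**5. True effects at d = 0.66** (100–1000 metabolites, one or two components, 108 settings per row, 400 runs each). Realised FDR, BH over survivors:

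| Truly different | Range | Median | Settings above 10% |
|---|---|---|---|
| 2% | 10–67% | 57% | 108 |
| 5% | 3–41% | 33% | 100 |
| 10% | 1–25% | 15% | 78 |
| 20% | 0.2–11% | 5% | 23 |

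BH over all metabolites gave 7–12% throughout; the gate with the full denominator gave 0.1–11%.

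**6. Sensitivity to effect size** (300 metabolites, block correlation 0.5, intraclass correlation 0.2–0.8, autoscaled, one predictive component, 300 runs). Realised FDR:

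| Truly different | Survivors, d = 0.66 | Survivors, d = 1.0 | Survivors, d = 1.5 | All metabolites, the three d values |
|---|---|---|---|---|
| 1% | 80% | 76% | 71% | 8–10% |
| 2% | 67% | 55% | 43% | 10–11% |
| 5% | 40% | 18% | 6% | 9–11% |
| 10% | 15% | 3% | 0.4% | 8–9% |
| 20% | 3.5% | 0.1% | under 0.1% | 7–8% |

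**7. Power when effects are widespread** (20% true, d = 0.66, autoscaled, one predictive component). The survivor rule declares about 34% of true effects, against 59% for BH over all.

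**The case against.** - **The excess depends on effect size.** This stands. At 5% true, FDR falls from 40% at d = 0.66 to 18% at d = 1.0 and 6% at d = 1.5. At 2% true it stays at 43% or more even for d = 1.5. What is lost is the guarantee; the rate is not exceeded in every case.
- **The no-effect scenario is the least expected.** Section 7 expects diet to shift the metabolome. That is fair, so the results with true effects matter more. They still show excess when few metabolites differ.
- **The inputs are assumptions.** This also stands. Ranges and counts of settings over a chosen grid show direction and plausible size; they are not probabilities.
- **BH may have been meant over all metabolites.** Then the rate holds approximately. But the plan describes models, and hence p-values, only for metabolites that pass the screen, and names no wider family. Reading identified as chemically identified does not fit, because the sentence directly follows the VIP cut-off.
- **It is a pilot producing candidate markers.** This lowers the consequence. The plan nevertheless states a numerical error rate for its primary aim.
- **The secondary aim is no clearer on its BH family.** True, so the contrast shows only that a primary set could be fixed in advance.

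**Conclusion.** The concern holds. On the natural reading of Section 7 and the Synopsis, BH is applied to metabolites preselected with the diet label, and FDR <0.10 is not controlled. With no diet effect, at least one false declaration is likely in most settings. With just-detectable effects (d = 0.66), the median realised FDR is 57% when 2% of metabolites differ and 33% when 5% do. When effects are strong or widespread the FDR falls below 0.10, but the gate then costs power. The size rests on assumed metabolite counts, scaling, correlation and VIP components. The loss of the guarantee does not: it follows from selecting and testing on the same contrast in the same samples. Because this is the error rate stated for the primary aim, it should be corrected before analysis.

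**What to change.** Fit the mixed model to every blood and urine metabolite that passes the CV and missingness filters, apply BH at 0.10 to that full set, and state whether blood and urine form one family or two. Section 5.1.1 also lists faecal metabolomics, so say whether those results fall outside the primary family. Use PCA, OPLS-DA and VIP for description.

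If the VIP gate is kept, state that the BH denominator is the full count of metabolites passing quality control, and accept lower power when effects are widespread: about 31% against 59% at 20% true (d = 0.66, autoscaled, one predictive component). In either case, state the scaling and the number of components used for VIP.

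The cost is one or two sentences in the plan and extra model fits; no new samples or participants. With sparse, modest effects the corrected rule declares fewer true metabolites: about 30% against 69% at 5% true, d = 0.66, same configuration. In the Step 6 setting at d = 1.0 the two are close, 87% against 89%. The extra yield under the current rule comes with uncontrolled false discoveries.
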